# RESUME\_STUDY Clinical study EOXY BIOSERENITY\_80601-2-61

Title	Clinical Trial testing the BioSerenity Pulse Oximeter (EOXY) efficacy, performance and safety in healthy volunteer
NCT	NCT03614416
Document date	05 june 2017

Objectives Primary objective: evaluate the SpO2 and HR accuracy of the Bioserenity	
Primary objective: evaluate the SpO2 and HR accuracy of the Bioserenity pulse oximeter (EOXY), evaluating the performance of the device compared to invasive method blood sampling (SaO2) by CO-Oximeter, and compared to a pulse oximeter gold standard.	
Secondary objective 1: measurement of the variation of the fraction of inspired oxygen (FiO2).	
Secondary objective 2: validation of the algorithm for data review and analysis of signal.	
Type: Wireless non-invasive and reflectance-based pulse oximeter developed by Bioserenity	
Description: As opposed to transmittance oximeters, the photodiodes of reflectance-based oximeters collect the light emitted by the LEDs and reflected (as opposed to crossing light) by the bones, tissues and muscles. The reflectance type pulse oximeters can perform measurement from various sites of the body, excluding the limitation of measurement position [1].	
Using of the device for the study: Intended to be used to acquire and transmit recorded data from adults. The EOXY permits non-invasive, continuous acquisition and monitoring of the pulse rate (PR) and of the oxygen saturation level in the blood (SpO2) of adults. For the study, it is intended to be used on different body site as the forehead, the chest or the back.	

Abstract\_EOXY Page 1 on 4

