### RESUME\_STUDY Clinical study EOXY BIOSERENITY 80601-2-61

#### Method

According to the European standard ISO 80601-2-61:2011, clinical investigation is conducted in order to assess the performance and safety of pulse oximeters, comparing the measured EOXY SpO2 values to SaO2 values collected by invasive methods using blood sampling, and comparing the EOXY heart rate values to goldstandard heart rate.

The EOXY SPO2 and HR measurements, is performed in O2 saturation conditions up to 100% and then in different desaturation plateaus, ranging from 100 % to 70%. Three EOXY pulse oximeters record the SpO2 and HR at the same time in 3 different body areas: chest, back-torso, forehead. Different body areas are tested in order to assess separately the safety and performance of the EOXY device on these areas. The EOXY SpO2 values is simultaneously compared to SaO2 measures providing from invasive blood sampling taken from an indwelling arterial catheter. The EOXY heart rate measures is compared to a gold standard oximeter CE-marked. The controlled desaturation is performed in five progressive plateaus from 100% to 70%. As the example given in the ISO standard, we choose to do the test on the 70-100% desaturation range, with 5 plateaus (100%-97%; 97%-92%; 92%-85%; 84%-78%; 77%-70%). 5 SPO2 values, 5 SaO2 values (blood samples) and 5 heart rate measures are collected per plateau, for each of 13 subjects.

The desaturation plateaus are reached using controlled FiO2 levels performed by a device. It permits to bring subjects near target levels of desaturation plateaus and to maintain them at the target plateau during the 5 blood samples.

A number of inclusions of 13 was chosen to have at least 10 subjects, in case of drop-outs or analysis exclusions. ISO 80601-2-61:2011 standard advices to collect 200 pairs of data.

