#### RESUME\_STUDY Clinical study EOXY BIOSERENITY\_80601-2-61

	7
	Exclusion criteria: - Smokers or individuals exposed to high levels of carbon monoxide that result in elevation of carboxy hemoglobin levels
	- Individual subject to conditions that result in elevated levels of methemoglobin
	- Subject who would be placed at undue medical risk associated with any procedure called for in the protocol
	- Subject with open wounds
	- Pregnant woman (negative pregnancy test needed)
	- Subject allergic to silicon, polyamide and silver yarn
	- Subject with cardiorespiratory disorders likely to worsen with thoracic pressure applied by the textile band
	- Subject with mental or motor impairment preventing him from expressing pain
	- Subject with blood or skin disorder that may impacting results
	- Subject with behavioral disorders, too agitated or too aggressive
	- Subject with sensorial disorders, insensible to skin pain
	- Subject susceptible to tension/pressure-based headaches
	No vulnerable subject is enrolled on this study.
Duration of participation and follow-up	Participation duration: 2 days (3 days for subjects of phase 1) No follow-up visit planned
End point criteria	Primary objective: -For performance: Collection of 5 different values of SpO2, SaO2 and HR after each desaturation plateau. These values are used for the analysis of the performance of the EOXY device and the performance of the gold standard, following the ISO 80601-2-61:2011 standardFor safety: Monitoring of vital sign: heart rate ( HR ) continuously, blood pressure and temperature between each desaturation plateau. Also, adverse events are collected during the study.
	Secondary objective 1: FiO2 is assessed to bring subjects near target levels of desaturation plateau. No analysis is performed on these data.
	Secondary objective 2 : Assessment thanks to the signal analysis. No data analysis performed
Statistical method	The clinical performance analysis for this study is assessed by the Accuracy Root-Mean square (ARMs) (calculated by the difference between the investigational pulse oximeter SpO2 measurement and the co-oximeter's SaO2 measurements) and is assessed by the Bland-Altman plot visualizing the difference between SpO2 and SaO2.

Abstract\_EOXY Page 3 on 4

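### Secondary objective 2 promises validation of the signal algorithm, but its endpoint entry plans no data analysis, so the plan can support no validation conclusion

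*Combined protocol and SAP*

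**What the plan says.** The Objectives table of the combined protocol and SAP lists "Secondary objective 2: validation of the algorithm for data review and analysis of signal". The End point criteria entry for that objective is, in full: "Assessment thanks to the signal analysis. No data analysis performed".

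The entry for secondary objective 1, on inspired oxygen, also excludes analysis: "No analysis is performed on these data". There, though, the document explains that FiO2 is a means of bringing subjects to the target plateaus.

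The Statistical method section begins "The clinical performance analysis for this study is assessed by the Accuracy Root-Mean square (ARMs" and continues with a Bland-Altman plot. Both concern the difference between device SpO2 and co-oximeter SaO2. The algorithm is not mentioned there.

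On data volume, the Method section says "5 SPO2 values, 5 SaO2 values (blood samples) and 5 heart rate measures are collected per plateau, for each of 13 subjects".

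**The concern.** To validate an algorithm is to show that its output agrees with a reference, or meets a criterion, to a stated degree. That requires an analysis. This plan does more than leave the analysis undescribed: it states that none is done. A team that followed it exactly would finish the trial with an objective worded as validation and no number behind it.

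What is at stake is the claim. A clinical report or technical file that lists the study's objectives could carry forward a statement that the algorithm was validated in 13 healthy volunteers, and a reader would have no planned result against which to check it.

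**Working it through.** The point rests on comparing text. The plan gives no figure for this objective, so there is none to reproduce.

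**1. Objective against endpoint**

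| Element needed for validation | Where it would appear | What is there |
|---|---|---|
| Claim | Objectives | Validation of the algorithm |
| Algorithm output to be judged | End point criteria | Not given |
| Reference | End point criteria, Method | None linked to this objective |
| Performance measure | Statistical method | None; ARMS and Bland-Altman are for SpO2 against SaO2 |
| Acceptance criterion | Anywhere | Not given |
| Analysis | End point criteria | "No data analysis performed" |

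The claim is present and everything that would support it is absent. The entry is also at odds with itself: it names signal analysis as the means of assessment and then says that no data are analysed.

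**2. Is lack of data the reason?** Inputs from Method: 5 plateaus, 5 readings per plateau, 13 enrolled to keep at least 10, and 200 pairs cited from the ISO standard. I read the 5 SpO2 values per plateau as applying to each body area, since three devices record at once.

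- All enrolled: 13 × 5 × 5 = 325 pairs per body area.
- Minimum retained: 10 × 5 × 5 = 250 pairs per body area.

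Both exceed 200. The gap is a missing analysis, not missing data.

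**3. Does the gap reach the primary analysis?** It would if the algorithm decided which readings enter ARMS. No section says that it accepts or rejects readings, and Statistical method states no signal-quality filter. The one mention of exclusions is "A number of inclusions of 13 was chosen to have at least 10 subjects, in case of drop-outs or analysis exclusions". That sentence is about keeping enough subjects and is not tied to the algorithm.

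**4. How large could such an effect be, if it existed?** Neither input is in the documents: I assume ARMS of 3.0 and 5% of readings rejected, with normal errors centred on zero.

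- Rejection unrelated to error: expected mean square unchanged, ARMS 3.0, reduction 0%.
- Exactly the largest 5% of absolute errors rejected: with c = 1.960 and normal density φ(c) = 0.0584, the retained mean square is multiplied by 1 − 2cφ(c)/0.95 = 1 − 0.229/0.95 = 0.759. ARMS = 3.0 × √0.759 = 2.61. Reduction = (3.0 − 2.61)/3.0 = 13%.

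The upper end cannot be reached in practice. Picking out exactly the largest errors requires knowing SaO2, and an algorithm working on the device signal does not have it.

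**The case against.** The strongest reply is that the entry does name a means of assessment. It can be read as a technical review of signals by engineers with no statistical analysis, parallel to the treatment of FiO2. The document is also a four-page summary, and detail may sit elsewhere. This stands in part: some review may well be intended. But a review with no measure or criterion does not amount to validation, and the summary points to no fuller plan for this objective. The parallel with FiO2 is weak, because objective 1 is worded as a measurement and objective 2 as a claim.

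A second reply is that ARMS tests the algorithm indirectly, since SpO2 may be its product. The documents do not say this. They list the two objectives separately, each with its own endpoint entry. If that is what is meant, one sentence would settle it.

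In the other direction, a reader might infer from the phrase about data review that the algorithm discards poor readings and so flatters the primary ARMS. The documents do not support that. No such mechanism is described, and the 13% above is only the extreme of a range that starts at zero.

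**Conclusion.** The inconsistency is real and follows from the document's own words. As written, the trial plans no estimate of algorithm performance and can support no validation conclusion for secondary objective 2. This conclusion depends on no sample size, error rate or outside figure.

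Its reach is limited. The objective is secondary, and nothing in the documents shows that the primary SpO2 accuracy result is compromised. It should be corrected before any statement about algorithm validation is made. The 0% to 13% range rests wholly on assumed inputs and an assumed mechanism, and should not be cited as an effect in this trial.

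**What to change.** Choose one of two routes.

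- **Reword.** State objective 2 as collection or technical review of signals, and make no validation claim. This costs one edit and the claim.
- **Analyse.** Replace the no-analysis statement with a defined one. Name the algorithm's output, the reference, the measure and the acceptance criterion. If the output is SpO2 or heart rate, the references are already collected: co-oximeter SaO2 and the gold-standard oximeter's heart rate. Report by body area, with intervals that allow for repeated readings within subject, for example by resampling whole subjects. If the output is the same SpO2 that enters the primary analysis, say so, so that one result is not counted as two. If the criterion is set after the data have been seen, label the analysis post hoc. This costs one extra table.

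Only if the algorithm accepts or rejects readings, and rejected readings are kept, add the share accepted out of the planned 25 per subject, and ARMS for accepted and for all readings. That comparison may look less favourable than ARMS on accepted readings alone. If the algorithm makes no such decisions, this table does not apply.

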# RESUME\_STUDY Clinical study EOXY BIOSERENITY\_80601-2-61

	ARMS is a representation of the combination of systematic and random error. It is defined as the accuracy root-mean-square error difference between the measured value and the truth value calculated as below, where "n" is the number of observations, and both SpO2 and SaO2 are defined as:
Safety assessment	Assessment of the number of undesirable effects
References	[1] Marcus Kramer, Aaron Lobbestael et al. Wearable Pulse Oximetry Measurements on the Torso, Arms, and Legs: A Proof of Concept; Military medicine 182(S1):92-98 · March 2017

Abstract\_EOXY Page 4 on 4

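### Does the plan need a named statistic for heart rate, and written acceptance limits, before its primary objective can be analysed?

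*Combined protocol and SAP*

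**What the plan says.** The Objectives row of the combined protocol and SAP sets out to "evaluate the SpO2 and HR accuracy of the Bioserenity pulse oximeter (EOXY"), which makes HR accuracy part of the primary objective alongside SpO2. The Method section describes "comparing the EOXY heart rate values to goldstandard heart rate" and names a CE-marked oximeter as the reference. It adds that "Three EOXY pulse oximeters record the SpO2 and HR at the same time in 3 different body areas", and that performance is judged separately by area. Five readings of each measure are planned at each of five plateaus in 13 subjects.

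The End point criteria row lists HR with SpO2 and SaO2 among the values collected. It assigns all of them to a performance analysis that follows ISO 80601-2-61:2011.

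The Statistical method row is narrower. It says "The clinical performance analysis for this study is assessed by the Accuracy Root-Mean square (ARMs"). It ties this figure to oxygen saturation alone, subtracting the blood-sample SaO2 from the EOXY SpO2. The second tool is tied to the same pair: performance "is assessed by the Bland-Altman plot visualizing the difference between SpO2 and SaO2". The continuation of the row says "ARMS is a representation of the combination of systematic and random error". It then describes Arms generally, as a root-mean-square difference between what is measured and what is true. The row ends with a lead-in to the formula, "both SpO2 and SaO2 are defined as". The formula itself is not in the text available for this review. No row states a numerical acceptance limit for HR or for SpO2.

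**The concern.** HR is the only item under the objectives that is to be analysed without a named method. SpO2 has Arms and the Bland-Altman plot. For inspired oxygen and for the signal algorithm, the End point criteria row says that no analysis will be done. HR falls between these, so its omission looks like an oversight rather than a decision.

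Read in isolation, the Statistical method row would return results for the SpO2 part of the primary objective and nothing for HR. Without a written limit, neither measure could be declared acceptable or unacceptable at any site from this document alone. A limit chosen after the data were seen could be chosen to suit them.

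**Working it through.** **1. What each row says about each item**

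| Item | Comparator | Analysis stated | Statistic named | Limit written |
|---|---|---|---|---|
| SpO2 | Co-oximeter SaO2 | Yes, under the ISO standard | Arms, Bland-Altman plot | None |
| HR | CE-marked reference oximeter | Yes, under the ISO standard | None | None |
| Inspired oxygen | – | None intended | – | – |
| Signal algorithm | – | None intended | – | – |

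HR therefore has data, a comparator and a stated route to analysis. What is missing is the name of the summary.

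**2. The plan's own count, then the HR data**

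Inputs from the Method section: 5 plateaus, 5 readings per plateau, 13 subjects enrolled to leave at least 10, and 200 pairs advised by the standard.

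- Readings per subject: 5 × 5 = 25.
- Per site with 10 subjects: 10 × 25 = 250. With 13 subjects: 13 × 25 = 325.
- Subjects needed for 200 pairs: 200 / 25 = 8.

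The stated design meets its own target. Assuming that each EOXY unit and the reference oximeter are read at every sampling time, HR has the same 250 to 325 pairs per site. These are repeated readings in 10 to 13 people, so they are not independent, but that is equally true of SpO2.

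**3. Whether the named methods carry over to HR**

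In its usual form, Arms = √[Σ(measured − reference)² / n]. Put EOXY HR for the measured value and reference-oximeter HR for the reference. The result is an Arms in beats per minute for each site, with n between 250 and 325. The Bland-Altman plot uses the same differences. Nothing further has to be collected, and the general description of Arms in the Statistical method row fits this use.

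**4. Whether the two methods could give conflicting verdicts**

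With the SD taken on divisor n, Arms² = bias² + SD², so Arms ≥ |bias|. A limit lying between |bias| and Arms would pass on bias and fail on Arms. That conflict arises only if bias is used as a criterion. The document gives Arms as the accuracy figure and the plot as a display of differences, and nowhere offers bias as a decision rule.

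**5. Size**

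Two measures at three sites make 6 primary results, of which 3 have a named statistic and none a limit. In pairs with 13 subjects, 325 × 3 = 975 for HR out of 2 × 975 = 1,950. With 10 subjects it is 750 of 1,500. Both fractions are one half, which only restates that there are two measures.

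**6. Limits**

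The document gives no alpha, power, SD or margin. The sample size rests on a count of pairs and not on a test, so no calculation in the plan depends on a limit and no pass or fail figure can be derived.

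**The case for a change.** The strongest case for a change is that a primary measure should not depend on inference. The reference to the ISO standard is general: it cites no clause, HR statistic or figure. The same document still spells out the SpO2 method, so the standard was evidently not thought sufficient there. The general description of Arms is followed at once by wording tied to SpO2 and SaO2. Even if the method is extended to HR, there is still no threshold. Writing both down would cost a few lines and no extra subjects or blood samples.

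Much of this stands as description. No sentence names an HR statistic, and no limit is written. It does not show a defective plan, for three reasons.

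- The text is labelled a study summary and an abstract, runs to four pages, and refers in its eligibility criteria to procedures set out in a protocol. It also mentions subjects of a phase 1 that it does not describe. Detail missing here may well exist in that fuller text.
- The stated aim is to evaluate accuracy. No hypothesis or success claim is made that would need a threshold.
- The sentence leading into the formula breaks off where the formula is missing, so it is weak evidence that Arms was meant for SpO2 only. The explicit SpO2 − SaO2 wording earlier in the row is firmer, but it does not exclude the obvious parallel use.

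One part of the worry cannot be settled here. If neither the ISO standard nor the fuller protocol fixes a limit, one could be set after the data are known. The documents do not show whether that is so.

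**Conclusion.** No change to the plan follows. The gap is real but is one of detail: HR has planned readings, a named comparator and a stated analysis route, and the summary that fits it is already described for SpO2. An analyst would report Arms in beats per minute and a Bland-Altman plot for each body site, on 250 to 325 pairs. No stated rule gives a wrong answer. Any added text would only record that obvious choice and a limit whose value the sponsor would have to supply.

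This rests on three assumptions: that HR is read on all devices at each sampling time, that analysts extend the named methods to HR as the End point criteria row implies, and that the ISO standard or the fuller protocol supplies any acceptance limit in use. The third cannot be checked from the documents. If it failed, the study could still describe accuracy for both measures, which is all that its objective claims. At most this is a minor reporting point.

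### Does the plan need changing because it names no confidence interval for bias or Arms at each body site?

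*Combined protocol and SAP*

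**What the plan says.** The Method section sets the amount of data: "5 SPO2 values, 5 SaO2 values (blood samples) and 5 heart rate measures are collected per plateau, for each of 13 subjects". There are five plateaus, and the gas control is meant to bring subjects near each target level and "to maintain them at the target plateau during the 5 blood samples". Three devices record at the same time on chest, back and forehead, and the sites are not to be merged: "Different body areas are tested in order to assess separately the safety and performance of the EOXY device on these areas".

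The size of the study is explained in two statements. One is about subjects: "A number of inclusions of 13 was chosen to have at least 10 subjects, in case of drop-outs or analysis exclusions". The other reports that the ISO "standard advices to collect 200 pairs of data".

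The Statistical method section names two tools. The first is Arms, in whose definition n "is the number of observations, and both SpO2 and SaO2 are defined as" (the formula that follows did not survive text extraction, and nothing here depends on it). The second is graphical: performance "is assessed by the Bland-Altman plot visualizing the difference between SpO2 and SaO2". No standard error, confidence interval, limits of agreement or treatment of repeated pairs is named. The End point criteria section says that the performance analysis follows ISO 80601-2-61:2011, whose content is not reproduced.

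**The concern.** Each site's result rests on few independent units. The 25 pairs from one person share that person's skin, anatomy and sensor placement, and the five pairs within a plateau share its conditions as well. The plan itself expects people to differ, since it requires at least two subjects with dark skin pigmentation. Yet Arms is defined over observations, and the only stated target for quantity of data, apart from the head count, is a number of pairs.

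A reader could therefore see three point estimates, each backed by several hundred pairs, and take them as firmer than 10 to 13 people can make them. An analyst who later added an interval might also use the pair count as the sample size and obtain one that is too narrow. At stake is how well the report conveys the precision of the primary result at each site.

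**Working it through.** **Inputs from the document (Method section).** Plateaus: 5. Pairs per plateau: 5. Subjects: 13 planned, at least 10 expected in the analysis. Pairs advised: 200.

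**Counts.**
- Pairs per subject at one site: 5 × 5 = 25.
- Pairs per site: 13 × 25 = 325, or 10 × 25 = 250.
- The advised 200 pairs would need 200 / 25 = 8 subjects, so the plan exceeds that number even at its minimum.

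The document gives no SD, margin, power or precision target, so it has no sample-size calculation to reproduce.

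**Assumptions, none of them in the document.** True Arms 3 points; zero mean bias; normal differences; equal correlation (ICC) between any two pairs from the same subject, taken as 0.1, 0.3 and 0.5.

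**Spread of the Arms estimate.** The variance of Arms² is inflated by 1 + 24 × ICC², which gives 1.24, 3.16 and 7.0. With N pairs, the relative standard error of Arms is about √(inflation / 2N). For 10 subjects and ICC 0.3 this is √(3.16 / 500) = 0.0795, and 1.96 × 0.0795 × 3 = 0.47, or roughly 2.53 to 3.47. Simulation, which does not need the large-sample approximation, gives the middle 95% of estimates:

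| Subjects | ICC 0.1 | ICC 0.3 | ICC 0.5 |
|---|---|---|---|
| 13 | 2.74–3.26 | 2.63–3.44 | 2.46–3.63 |
| 10 | 2.72–3.30 | 2.59–3.50 | 2.39–3.72 |

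The mean estimated Arms in these simulations is 2.98 to 3.00, so clustering does not bias the planned estimate in any material way.

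**Precision of bias.** The variance inflation is 1 + 24 × ICC, which gives 3.4, 8.2 and 13. The subject-level 95% half-width, in units of the SD of the differences, is t × √(inflation / N), with t on subjects minus 1 degrees of freedom. For 10 subjects and ICC 0.3: 2.262 × √(8.2 / 250) = 0.41. Over the three ICC values the results are 0.26, 0.41 and 0.52 with 10 subjects, and 0.22, 0.35 and 0.44 with 13. A t interval on the subject means covered 95% in simulation. It needs only one mean difference per subject, which the planned data supply.

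**Limits of agreement.** If drawn on the plot from the plain SD, they come out only 0.4% to 2.4% narrower than repeated-measures limits. The planned plot is little affected.

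**Would fixing an Arms method in advance help?** Two candidates were checked.
- Resampling subjects with percentile limits covered 83% to 91% over 10 and 13 subjects.
- Combining chi-square limits for subject, plateau-within-subject and residual components (MOVER) covered about 95% at zero bias and 95% to 96% at a 1-point bias. At a 2-point bias it covered more than 99%, with a mean width of about 1.5 points against 0.86 at a 1-point bias (13 subjects). With heavy-tailed subject effects it covered 83% to 89%.

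Neither is reliable over the whole range of plausible data. Writing one recipe into the plan now would not clearly improve on a choice made by an analyst who respects the subject as the unit.

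**The case for a change.** The strongest case for a change is that this is the primary analysis, the sites are to be judged separately, and one sentence would settle the matter at no cost in subjects or samples. Without it, a reader cannot tell whether an observed Arms of 3 is compatible with about 2.6 or 3.5. Choosing an interval method after the data are in also leaves room for the narrower option. With 10 subjects and ICC 0.3, the half-width for bias would be 0.12 SD if pairs were treated as independent, against 0.41 SD by subject. The reference to the ISO standard does not answer this, because the document does not say that the standard supplies an interval.

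Much of that stands. The omission is real, the counts are right, and a site-by-site interval using the subject as the unit would make a better report. But the too-narrow interval is one that nobody planned. The document draws no precision claim from 250 or 325 pairs; those totals do not appear in it, and its own reason for 13 inclusions is given in subjects. The text is also a four-page summary with two short paragraphs on statistics, so its silence on an interval is weak evidence about what will be reported.

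**Conclusion.** No change to the plan follows. The two named analyses give sound estimates, the sites are already kept apart, nothing planned misuses the pairs, and no stated conclusion could reverse. What is missing is a statement of precision, and it can be calculated later from the same data. Reporting bias and Arms for each site with intervals by subject would be good practice and is an optional recommendation.

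The unreported uncertainty is moderate. With 10 subjects and a true Arms of 3 points, the middle 95% of estimates runs from about 2.7–3.3 (ICC 0.1) to 2.4–3.7 (ICC 0.5). These ranges depend on the assumed Arms, zero bias and ICC. The absence of an interval and the count of 10 to 13 independent subjects do not. The conclusion would need another look if a fuller protocol set an acceptance limit to be met by an interval, or specified an interval computed from pairs as if they were independent.
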